11.2 Serious Adverse Events

11.2.1 DEFINITION: Fed. Reg. 75, Sept. 29, 2010 defines SAEs as those events, occurring at any dose, which meet any of the following criteria:

- Results in death
- Is life threatening (Note: the term life threatening refers to an event in which the patient was at risk of death at the time of the event; it does not refer to an event that hypothetically might have caused death if it were more severe).
- Requires inpatient hospitalization or prolongation of existing hospitalization
- Results in persistent or significant incapacity or substantial disruption of the ability to conduct normal life functions
- Is a congenital abnormality/birth defect
- Important medical events that may not result in death, be life-threatening or require hospitalization may be considered serious when, based upon appropriate medical judgment, they may jeopardize the patient or subject and may require medical or surgical intervention to prevent one of the outcomes listed.

11.2.2 Reporting SAEs to DCP

11.2.2.1 The Consortium Lead Organization and all Participating Organizations will report SAEs on the DCP SAE form found at http://prevention.cancer.gov/files/clinical-trials/SAE_form.doc.

11.2.2.2 Contact the DCP Medical Monitor by phone within 24 hours of knowledge of the event.

[name]
Prostate and Urologic Cancer Research Group
Division of Cancer Prevention, National Cancer Institute, NIH, DHHS
Shady Grove Campus
[name]
[name]
[contact]
[contact]

Include the following information when calling the Medical Monitor:

- Date and time of the SAE
- Date and time of the SAE report
- Name of reporter
- Call back phone number
- Affiliation/Institution conducting the study
- DCP protocol number
- Title of protocol
- Description of the SAE, including attribution to drug

11.2.2.3 A written SAE report will be faxed to the DCP Medical Monitor within 48 hours of learning of the event using the paper SAE form. PO's will submit their written report to the CLO for review via [contact]) or e-mail ([contact]). Staff at the CLO will review the SAE report form and will return it to the PO if any revisions are required. Once approved, the CLO will FAX the report to the DCP Medical Monitor and to DCP's Regulatory Contractor, CCS Associates, at [contact] ([contact]) or e-mailed to [contact].

11.2.2.4 The DCP Medical Monitor and regulatory staff will determine which SAEs require FDA submission.

11.2.2.5 The Lead Organization and all Participating Organizations will comply with applicable regulatory requirements related to reporting SAEs to the IRB/IEC.

11.2.2.6 Follow up of SAE
PO staff should send follow-up reports as requested when additional information is available. Additional information should be entered on the

DCP SAE form in the appropriate format. Any information that is added to the report should be circled and dated. Any information that is deleted from the original report should be struck through and dated. Follow-up information should be sent to DCP as soon as available. PO's will submit their follow-up forms to the CLO for review. Once approved, the CLO will submit the follow-up form to the DCP. SAEs will be followed until resolution to baseline, or until the study is closed to accrual, whichever comes first.

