3. SUMMARY OF STUDY PLAN

Study Design

Eligible individuals must be at least 21 years of age or older, with a low-grade, clinically localized prostate cancer. Individuals must have had a prostate biopsy within 13 months of study entry. Use of 5 α reductase inhibitors is prohibited during the study, and for six months prior to the baseline study visit.

Thirty participants will be accrued to this study. Participants will be stratified by tumor volume (≤ 2 positive cores and $\leq 10\%$ of any biopsy core volume is adenocarcinoma vs. >2 positive cores or $> 10\%$ of any biopsy core volume is adenocarcinoma). We expect an enrollment duration of 12-18 months. Participants will be randomized, in a 1:1 ratio, to one of two treatment groups:

PFE (as POMx™) 1000mg (i.e., one (1) 1000mg capsule) taken each morning, by mouth, for 52 weeks ± 1 week

Placebo (0mg PFE) one (1) capsule taken each morning, by mouth, for 52 weeks ± 1 week

Following the baseline visit, participants will return for evaluation at 13, 26, 39 and 52 weeks. Scheduled evaluations/procedures are as follows:

- **Baseline Visit:** Eligibility, safety labs and total PSA (to be processed at the PO's clinical lab). Medical history, physical exam, review of concomitant medications and baseline symptom assessment. Blood and urine collection for research purposes (to be batch shipped when a participant completes the study for analysis by the CP lab at UWI. Analysis will include total serum PSA for doubling time, serum testosterone, plasma pharmacokinetics, plasma biomarkers, and urine pharmacokinetics). Review of the pre-study biopsy clinical pathology report for verification of the presence of adenocarcinoma, confirmation that the Gleason grade meets study eligibility criteria, and for stratification by tumor volume. Participants will be stratified by tumor volume and randomized to one of the two treatment groups.
- **Week 13 and 39 Visits:** Safety labs and total PSA (to be processed at the PO's clinical lab), review of adverse events and concomitant medications, pill count and compliance review, blood and urine collection for research purposes (batch shipped to the CP lab at UWI for analysis of total serum PSA, plasma pharmacokinetics and biomarkers and urine pharmacokinetics).

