7.2.2 Study Registration

Once a participant has signed a consent form, he is assigned a participant ID (PID) number and is considered registered to the study. PID numbers are assigned sequentially and designate the recruitment site, the study and the participant. The CLO will provide each PO with a Participant Identification Number Log at the time of study initiation. Once a participant is registered, the CLO will be notified immediately, to ensure timely and accurate tracking of accrual. [contact]) or e-mail ([contact]) a copy of the Baseline Visit Guide and the Eligibility Questionnaire to the CLO.

If a consented participant is deemed ineligible (a screen failure), the following documents (provided to PO's at study initiation) must be completed and submitted to the CLO:

- the Baseline Visit Guide
- the Eligibility Questionnaire
- a de-identified copy of the participant's informed consent form
- an Off Study Form
- a Verification Form
- an Adverse Event Tracking Worksheet. If the participant has not experienced an adverse event during the screening process or as a result of baseline study visit procedures, check the box at the top of the page.

Participants will be registered in the OnCore database by CLO staff.

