7.5 Post-intervention Follow-up Period

There is no post-intervention follow-up period for this study.

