8.4 Off-Study Criteria

Participants may go off study for the following reasons: the protocol intervention and any protocol required follow-up period is completed, AE/SAE, lost to follow-up, non-compliance, concomitant medication, medical contraindication, withdrawal of consent, determination of ineligibility, or death. Off study will mean that the investigator will not be able to or does not need to follow the participant to complete any measurements.

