11.1.5 Follow-up of AEs

All AEs, including lab abnormalities that in the opinion of the investigator are clinically significant, will be followed according to good medical practices and documented as such.

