13.2 Sample Size/Accrual Rate

The sample size for each group is based on comparing the change in IGF-1 levels between the PFE and placebo arms. According to ELISA assay analysis, this primary endpoint can be considered a continuous random variable. The sample size justification is thus based on a two-tailed two-sample t-test of the difference between the two groups at a significance level of 0.05. In order to detect an effect size of 1.10, i.e. the difference in the mean change between the two groups of 1.10 standard deviations, with power 0.80, or an effect size of 1.17 with power 0.85, the trial requires an effective sample size of 14 per group. Assuming a random dropout of up to 5%, 15 subjects per group will be enrolled for a total of 30 subjects for this exploratory study.

There will be six organizations participating in the study. With each PO randomizing one participant per month, a conservative estimate, the study will enroll the target accrual goal of 30 subjects within 6 months. Considering the usual delay due to start-up, it may take up to 18 months. Each randomized participant will be treated with study medication for one year. We will allow for a study duration of two-three years.

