13.7 Evaluation of Toxicity

All participants receiving any protocol treatment will be evaluated for toxicity from the time of their first dose of placebo or PFE up to the time of biopsy according to the NCI's Common Terminology Criteria for Adverse Events (CTCAE) version 4.0.

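### Section 11.2.2.6 ends SAE-specific follow-up at closure to accrual, an enrolment date, when the last man enrolled still has about 52 weeks of dosing and a biopsy ahead

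*Combined protocol and SAP*

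**What the plan says.** The last sentence of 11.2.2.6 sets the stop rule for SAE follow-up: "SAEs will be followed until resolution to baseline, or until the study is closed to accrual, whichever comes first". Earlier sentences in the same section, which carry no date, ask sites for follow-up reports on request and for new information to be forwarded when it becomes available.

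Section 11.1.5 covers adverse events in general: "All AEs, including lab abnormalities that in the opinion of the investigator are clinically significant, will be followed according to good medical practices". It gives no cut-off.

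On timing, Section 3 states: "We expect an enrollment duration of 12-18 months". Section 13.2 allows for accrual as fast as 6 months or as slow as 18, and adds: "Each randomized participant will be treated with study medication for one year". Section 7.1 places the end-of-study biopsy at week 52, plus or minus a week, or at discontinuation of study therapy. Section 7.5 states: "There is no post-intervention follow-up period for this study".

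**The concern.** The stop rule uses the wrong clock. A follow-up duty for serious events would normally run to an outcome, or to a date tied to the participant's own exposure. Closure to accrual is neither: it falls when the last man joins. Because the earlier of the two dates governs, the enrolment date overrides an event that has not resolved.

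The result is also back to front. On the face of the text, a serious event can lose its specific follow-up instruction while a non-serious event, under 11.1.5, has no stated end to its follow-up. At stake is whether a site must, without being asked, pursue an unresolved SAE to its outcome and keep the sponsor's SAE form current.

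**Working it through.** **What accrual means in this protocol.** Section 7.2.2 ties the word to registration: "Once a participant is registered, the CLO will be notified immediately, to ensure timely and accurate tracking of accrual". Section 13.2 uses it for the target of 30 enrolled subjects. Both uses are enrolment; neither refers to completion of treatment.

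**The plan's own timing figures.** Six organizations at one man a month give 30 / 6 = 5 months, consistent with the stated 6. Adding 12 months of treatment to accrual of 6, 12 or 18 months gives 18, 24 or 30 months. The last two fit the two to three years allowed in 13.2. Closure to accrual therefore comes about a year before the last man finishes, whatever the accrual rate.

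**Who is still on agent at closure.** The documents give only ranges for accrual, so I assume uniform entry over A months and no dropout. A man entering at month u is treated from u to u + 12, and accrual closes at month A.

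- Men on agent at closure = 30 × min(1, 12/A). Each of them also has his week-52 biopsy still to come.
- For A ≤ 12, mean time left is 12 − A/2 months. For A = 18, the men still on agent have a mean of 6 months left.
- Total planned dosing is 30 × 12 = 360 man-months.

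| Accrual (months) | On agent at closure | Man-months of dosing after closure | Share of 360 |
|---|---|---|---|
| 6 | 30 | 30 × 9 = 270 | 75% |
| 12 | 30 | 30 × 6 = 180 | 50% |
| 18 | 30 × 12/18 = 20 | 20 × 6 = 120 | 33% |

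Placing 30 men at equally spaced entry times instead gives 273, 186 and 126 man-months (76%, 52%, 35%), which is the same picture. The last man has the full 12 months left in every row. These are shares of exposure. They are not shares of SAEs, and the documents give no SAE rate for this population.

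**What stops at closure and what continues.**

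- Stops, read literally: the SAE-specific instruction to follow to resolution, both for events open at closure and for events that start later.
- Continues: the telephone report within 24 hours and written report within 48 hours (11.2.2); recording of event end date and outcome (7.3.1.3, 11.1.2); general AE follow-up (11.1.5); the undated sentences in 11.2.2.6; the stop-drug rule for any grade 3 or 4 event (5.6); and safety review about every six months (12.4, 13.9).

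**The case against.** The best reply is that little turns on this sentence. SAEs are AEs, so 11.1.5 already requires them to be followed, and follow-up on the sponsor's request is part of 11.2.2.6 both before and after closure. The wording may simply be a slip for closure of the study. Section 12.4 also imports a consortium monitoring plan that is not among the documents and could set its own SAE rule.

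Most of this stands and limits the size of the point. It does not remove it. Section 11.1.5 names no endpoint and does not mention the SAE form, and a site faced with a general clause and a specific one may reasonably apply the specific one. No section of the protocol resets the date. If the wording is a slip, that is a reason to correct it.

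Three stronger readings are tempting and are not supported.

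- *SAE oversight ends at closure.* It does not; the continuing duties listed above carry no accrual date.
- *Sections 8.4 and 13.7 also cut off SAE follow-up.* Section 8.4 says "Off study will mean that the investigator will not be able to or does not need to follow the participant to complete any measurements", which concerns study measurements. Section 13.7 evaluates toxicity "from the time of their first dose of placebo or PFE up to the time of biopsy", which sets an evaluation window. Neither limits how long an SAE is followed. The absence of contact after biopsy comes from 7.5 and would remain if only the accrual wording were changed.
- *The cardiac events in 6.2 size the gap.* Their seriousness is not stated, some arose at 3000 mg, which is not used here, and that study had no placebo group, whereas half of these men receive placebo. They cannot give a number of affected SAEs.

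**Conclusion.** The stop rule in 11.2.2.6 is wrong as written and inconsistent with 11.1.5. The mismatch in timing is large: depending on accrual, 20 to 30 of the 30 men would be on agent when the rule expires, assuming uniform accrual and no dropout. That the last man has about 52 weeks left needs only that he completes treatment.

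The consequence is small. It is confined to safety follow-up of SAEs that are unresolved at closure or begin afterwards, and even for those the general duty and sponsor requests remain. The comparison in 13.5 of presence, worst grade and attribution of toxicity does not depend on this sentence, nor do the primary endpoint and the power calculation. The number of events affected cannot be estimated from the documents. The conclusion is also subject to the monitoring plan cited in 12.4, which may already cover the point.

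**What to change.** Replace the last sentence of 11.2.2.6 with: *Each SAE, including any open at or arising from the end-of-study visit or biopsy, will be followed to resolution to baseline or stabilization, death, withdrawal of consent or loss to follow-up, regardless of accrual status.* The listed exceptions are needed because a duty that ends only at resolution cannot be met in those cases.

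Add a matching clause to 7.5 saying that SAE follow-up may continue after the final visit. Check that the monitoring plan cited in 12.4 says the same.

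The cost is a short amendment to two sections and a few follow-up contacts in a 30-man study, some possibly after the last visit. No sample-size or analysis change follows.

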12. STUDY MONITORING

12.1 Data Management

All of the procedures outlined in the University of Wisconsin chemoprevention consortium standardized Data Management Plan (approved 06/03/2013) will be followed in this protocol. Please refer to this document for additional details on data management procedures.

This study will report clinical data using the CLO's OnCore database (a web-based clinical trials/database). OnCore will be the database of record for the protocol and subject to NCI and FDA audit. Data entry will be performed at the CLO where staff is trained in OnCore per our DMP and applicable regulatory requirements such as 21 CFR; Part 11.

In order to standardize the collection of information, the CLO will provide POs with protocol specific Visit Guides.

12.2 Case Report Forms

Participant data will be documented in the University of Wisconsin's OnCore database using protocol-specific electronic case report forms (e-CRFs) developed from the standard set of DCP Chemoprevention CRF Templates and utilizing NCI-approved Common Data Elements (CDEs). CLO staff will enter data into OnCore and transfer to Federal Security Compliant formats for transmission to DCP according to pre-established DCP standards and procedures. Amended e-CRFs will be submitted to the DCP Protocol Information Office for review and approval.

12.3 Source Documents

In order to standardize the collection of study data, the CLO will provide POs with study-specific Visit Guides. These Visit Guides will provide instructions for conducting each study contact and specific details on the data to be collected and reported at each contact. All data reported must be documented either on a clinical primary source document (physician's notes, medication lists, nurse's and study coordinator's notes, pathology reports, operative reports, etc.,) or on the documents provided with the Visit Guides. All source documents must be signed by the staff that collected or elicited the information in the source documents. Source documents will be completed at each PO, then submitted to the CLO (either by fax, e-mail or US mail) for entry into the Oncore database.

12.4 Data and Safety Monitoring Plan

All of the procedures outlined in the University of Wisconsin Chemoprevention Consortium Phase I & II Clinical Trials of Cancer Chemoprevention Agents Data and Safety Monitoring Plan version 2: 01/19/2013 (DCP Approved 02/26/2013) will be followed in this protocol. The UW Chemoprevention Consortium Data and Safety Monitoring Committee will meet approximately every 6 months to review all data from ongoing consortium studies. In open session (may be attended by any member of the Consortium study teams in addition to the Consortium statistician), issues relating to the general conduct and progress of the study will be discussed (e.g. accrual, quality control, compliance with protocol, currency of follow-up, comparability of groups on baseline factors etc.). In closed session DSMC members and the Consortium statistician only review protocol safety data and efficacy endpoint, (if relevant). The data will be presented by coded treatment arm. The codes are accessible to the DSMC at any time if needed.

12.5 Sponsor or FDA Monitoring

The NCI, DCP (or their designee), pharmaceutical collaborator (or their designee), or FDA may monitor/audit various aspects of the study. These monitors will be given access to facilities, databases, supplies and records to review and verify data pertinent to the study.

12.6 Record Retention

Clinical records for all participants, including all source documentation (containing evidence to study eligibility, history and physical findings, laboratory data, results of consultations, etc.), as well as IRB records and other regulatory documentation will be retained by the Investigator in a secure storage facility in compliance with Health Insurance Portability and Accountability Act (HIPAA), Office of Human Research Protections (OHRP), Food and Drug Administration (FDA) regulations and guidances, and NCI/DCP requirements, unless the standard at the PO is more stringent. The records for all studies performed under an IND will be maintained, at a minimum, for two years after the approval of a New Drug Application (NDA). For NCI/DCP, records will be retained for at least three years after the completion of the research. NCI will be notified prior to the planned destruction of any materials. The records should be accessible for inspection and copying by authorized persons of the Food and Drug Administration. If the study is done outside of the United States, applicable regulatory requirements for the specific country participating in the study also apply.

12.7 Cooperative Research and Development Agreement (CRADA)/Clinical Trials Agreement (CTA)

This section is not applicable.

13. STATISTICAL CONSIDERATIONS

13.1 Study Design/Endpoints

This is a Phase IIA randomized, placebo-controlled, double-blind trial of modulation of intermediate endpoint biomarkers by PFE as POMx™ in subjects undergoing AS for low grade, early stage prostate cancer for 12 months. Participants will be randomized to placebo or PFE as POMx™ given for 12 months in a 1:1 ratio stratified by tumor volume.

The primary endpoint for modulation of intermediate endpoint biomarkers will be the change in the plasma levels of IGF-1 by a quantitative assay (ELISA) from pre-study to post-treatment.

The secondary endpoints include compliance and toxicity over the study duration, plasma biomarkers such as IGFBP-3, IGF-1/IGFBP-3 ratio, total PSA (serum), tissue (normal, normal adjacent to tumor, and abnormal prostate) biomarkers such as PSA, IGF-1, IGFBP-3, apoptosis (CASPASE 3), Ki-67, IGF-1R, 80HdG, and AR. Also, the following PFE constituents/metabolites will be measured for evidence of accumulation (trough levels): ellagic acid, dimethyl ellagic acid, dimethyl ellagic acid glucuronide (DMEAG), urolithin A, urolithin A glucuronide, urolithin B and urolithin B glucuronide.

The primary analysis will be a comparison of change in IGF-1 plasma levels from pre-study to post-study, based on two-sample t-test with normalizing transformation if necessary or Wilcoxon rank-sum test.

13.2 Sample Size/Accrual Rate

The sample size for each group is based on comparing the change in IGF-1 levels between the PFE and placebo arms. According to ELISA assay analysis, this primary endpoint can be considered a continuous random variable. The sample size justification is thus based on a two-tailed two-sample t-test of the difference between the two groups at a significance level of 0.05. In order to detect an effect size of 1.10, i.e. the difference in the mean change between the two groups of 1.10 standard deviations, with power 0.80, or an effect size of 1.17 with power 0.85, the trial requires an effective sample size of 14 per group. Assuming a random dropout of up to 5%, 15 subjects per group will be enrolled for a total of 30 subjects for this exploratory study.

There will be six organizations participating in the study. With each PO randomizing one participant per month, a conservative estimate, the study will enroll the target accrual goal of 30 subjects within 6 months. Considering the usual delay due to start-up, it may take up to 18 months. Each randomized participant will be treated with study medication for one year. We will allow for a study duration of two-three years.

